Excessive blood loss from heavy menses may result in iron deficiency anemia. Anemia is defined by the World Health Organization (WHO) as a hemoglobin (Hgb) concentration < 12 g/dL (120 g/L) for nonpregnant women, 15 years of age and above, at sea level.⁸ Subjects entering the study with anemia or who develop anemia during the study, if not already taking iron supplements, should be prescribed iron supplementation by the investigator as per standard of care. If the Investigator does not prescribe iron supplements for subjects with a Hgb < 12g/dL, the reason should be documented in source documents.

During Screening, all subjects with an Hgb level < 7 g/dL will be retested after receiving iron supplements; these subjects will only be eligible to randomize if their Hgb results meet eligibility prior to Day 1 (randomization) and they have not required a blood transfusion within 60 days prior to Day 1. All iron supplements taken during the study, from Screening through the Final Visit, must be recorded on the concomitant medications eCRF.

Concomitant Use of Corticosteroids and Other Medications

Chronic use (> 14 days) of systemic corticosteroids within 3 months prior to Screening through PTFU period is prohibited. Short-term use (no longer than 1 week [total of 7 days] per occurrence) of systemic glucocorticoids/corticosteroids to manage acute conditions is allowed during the Treatment Period. A maximum of 14 days over the 6-month Treatment Period is allowed during a subject's participation. Inhaled corticosteroids for the treatment of asthma are permitted. Over-the-counter and prescription topical, inhaled, intranasal, or intra-articular injectable (for occasional use) corticosteroids are allowed.

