### **Hemoglobin Concentration**

Hemoglobin (Hgb) concentration data will be summarized as observed; missing data will not be imputed.

Baseline Hgb concentration is defined as the last measurement prior to or on the first dose date of study drug. The change and percent change from Baseline in Hgb concentration to each of Months 1 – 6 during the Treatment Period will be analyzed with one-way ANCOVA with treatment group as the main effect and Baseline as a covariate.

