## 9.0 Safety Analyses

### 9.1 General Considerations

Safety data will be summarized for the Safety Analysis Set. Safety summaries will be presented by treatment group. For the safety analysis, subjects are assigned to a treatment group based on the treatment actually received, regardless of the treatment randomized. If

a subject received more than one type of study drug, safety data will be analyzed in the treatment group to which she was randomized to. All safety analyses will be based on observed data. For analyses of safety endpoints, subjects who are missing an evaluation will not be included in the analysis of that particular parameter/visit, unless otherwise specified.

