### **9.3 Analysis of Laboratory Data**

Data collected from central and local laboratories, including additional laboratory testing due to an SAE, will be used in all analyses, except for Baseline where SAE-related laboratory assessments on or before the first dose of study drug will be excluded. The clinical laboratory tests defined in the protocol operations manual (e.g., hematology and clinical chemistry) will be summarized.

Each laboratory variable will be summarized for all time points (starting with Baseline) with the number of non-missing observations, mean and standard deviation, median, minimum and maximum.

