#### **Laboratory Data in the Treatment Period**

Mean change from baseline to each applicable post-baseline visit will be summarized for selected laboratory variables, with the number of observations, baseline mean, and visit mean. The change from baseline mean, standard error, and 95% confidence interval will be presented for the mean change from baseline within each treatment group and difference between treatment groups (elagolix vs. placebo). The selected laboratory variables include the following: lipid variables, liver variables (alkaline phosphatase,

ALT, AST, bilirubin), glucose, hemoglobin, hematocrit, platelet count, and Red Blood Cell (RBC) count. For lipid variables, in addition to low-density lipoprotein cholesterol (LDL-C), high-density lipoprotein cholesterol (HDL-C), total cholesterol, and triglycerides (TG), the following ratios will be included: the ratio of total cholesterol to HDL-C, the ratio of LDL-C to HDL-C, the ratio of TG to HDL-C, and the ratio of non-HDL-C (calculated as total cholesterol minus HDL-C) to HDL-C.

Changes in selected laboratory parameters will be tabulated using shift tables either by NCI CTC criteria or categorized as low, normal, or high based on the normal ranges of the laboratory used for each sample. For those analytes that are not reflected in the NCI CTC criteria, exceptions to standard CTC lab grading criteria for elagolix studies will be used as specified in [Appendix C](#). A shift table from baseline either to the worse value (based on NCI CTC criteria) during treatment or to minimum and maximum value (based on normal range), will be created. A similar shift table will be provided to summarize shifts from baseline to the final post-baseline value.

Laboratory abnormalities meeting CTC criteria grade 3 and 4 will be summarized.

The number and percentage of subjects meeting the following criteria will be summarized at Baseline and each applicable visit by treatment group in the Treatment Period:

- Total cholesterol:  $\leq 300$ ,  $> 300 - \leq 400$ ,  $> 400 - \leq 500$ , and  $> 500$  mg/dL
- HDL-C:  $< 40$  and  $\geq 40$  mg/dL
- LDL-C:  $< 130$ ,  $\geq 130 - < 160$ ,  $\geq 160 - < 190$ , and  $\geq 190$  mg/dL
- TG:  $\leq 150$ ,  $> 150 - \leq 300$ ,  $> 300 - \leq 500$ ,  $> 500 - \leq 1000$ , and  $> 1000$  mg/dL
- LDL-C/HDL-C ratio:  $\leq 3$ , and  $> 3$
- Total cholesterol/HDL-C ratio:  $\leq 4.5$ , and  $> 4.5$ .

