#### **9.4 Analysis of Vital Signs**

Vital sign measurements of systolic and diastolic blood pressure, pulse rate, and body temperature will be summarized.

Each vital sign variable will be summarized for all time points (starting with Baseline) with the number of non-missing observations, mean and standard deviation, median, minimum and maximum. Mean change from baseline to each applicable post-baseline visit will be summarized for each vital sign variable, with the number of observations, baseline mean, and visit mean. The change from baseline mean, standard error, and 95% confidence interval will be presented for the mean change from baseline within each treatment group and difference between treatment groups (elagolix vs. placebo).

The number and percentage of subjects who have PCS vital sign values meeting the following criteria will be summarized by treatment group and a listing of these subjects will be provided. All increase/decrease will be calculated from Baseline to a post-baseline visit in the Treatment Period.

The number and percentage of subjects who have a sustained PCS vital sign value will be summarized by treatment group and a listing of these subjects will be provided. A sustained PCS value is defined as 3 consecutive PCS values in the Treatment Period.

- Diastolic blood pressure
  - $\leq 50$  mmHg and  $\geq 15$  mmHg decrease

- > 90 mmHg and  $\geq$  15 mmHg increase
- $\geq$  100 mmHg
- Systolic blood pressure
  - $\leq$  90 mmHg and  $\geq$  20 mmHg decrease
  - $\geq$  140 mmHg and  $\geq$  20 mmHg increase
  - $\geq$  160 mmHg
- Pulse rate
  - $\leq$  45 bpm and  $\geq$  15 bpm decrease
  - > 100 bpm and  $\geq$  15 bpm increase
  - $\geq$  120 bpm

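### SAP 9.3 and 9.4 specify no Baseline adjustment for elagolix–placebo differences in laboratory and vital-sign change, and hemoglobin gets two between-group estimates with nothing saying which to interpret

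*SAP*

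**What the plan says.** SAP 9.3 (Laboratory Data in the Treatment Period) presents the mean change from Baseline, its standard error and a 95% confidence interval "for the mean change from baseline within each treatment group and difference between treatment groups (elagolix vs. placebo"). The selected variables are lipids, liver tests and other parameters, among them "ALT, AST, bilirubin), glucose, hemoglobin, hematocrit, platelet count, and Red Blood Cell (RBC) count". SAP 9.4 uses the same form for vital signs: "The change from baseline mean, standard error, and 95% confidence interval will be presented for the mean change from baseline within each treatment group", and likewise for the difference between groups. Neither section names a model, a covariate or a p-value. SAP 9.1 adds only this: "All safety analyses will be based on observed data".

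Hemoglobin change also appears in SAP 8.4 as an efficacy variable. There it "will be analyzed with one-way ANCOVA with treatment group as the main effect and Baseline as a covariate".

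Baseline is worded differently in the two places. In 8.4: "Baseline Hgb concentration is defined as the last measurement prior to or on the first dose date of study drug". In 9.3, all central and local laboratory data are used, "except for Baseline where SAE-related laboratory assessments on or before the first dose of study drug will be excluded". Operations Manual 3.8 gives a third wording, taking the results obtained before Day 1 as Baseline, although the activity schedule includes hematology on Day 1.

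**The concern.** Each of these parameters has a Baseline value, and the SAP names Baseline as a covariate wherever it plainly intends one: the MMRM (8.2), the primary logistic model (8.3.3), and the ANCOVAs for menstrual blood loss, hemoglobin and UFS-QoL (8.4). Against that pattern, its absence from 9.3 and 9.4 reads as an unadjusted difference in mean change. With only 16 placebo women planned, an avoidable loss of precision in the safety comparisons is worth noting.

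Hemoglobin adds a problem of consistency. The full analysis set and the Safety Analysis Set have the same membership rule (randomised, at least one dose). Scheduled on-treatment hematology falls at Month 3, Month 6 and the premature discontinuation visit. So the report will carry two elagolix–placebo differences for essentially the same changes, one adjusted and one not, with no rule for choosing between them. Adjustment has a specific rationale for this variable, because Protocol 5.4 says "Subjects entering the study with anemia or who develop anemia during the study, if not already taking iron supplements, should be prescribed iron supplementation". Change in hemoglobin therefore plausibly depends on the starting value in both arms.

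**Working it through.** **Inputs.** 32 elagolix and 16 placebo (SAP 2.4). The correlation ρ between Baseline and follow-up is not in the documents, so it is an assumption, shown over a range. Baseline and follow-up SDs are assumed equal (σ).

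**The plan's own figure.** No document figure describes the precision of the safety intervals. The only figure tied to the sample size is at least 80% power with 48 subjects at 10% versus 55%. It reproduces: a two-proportion calculation with continuity correction gives 16 placebo plus 32 elagolix, and power at 32:16 is 91.1% (pooled normal approximation) or 86.5% (Fisher's exact test).

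**Interval width.** Let k = √(1/32 + 1/16) = 0.306.

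- Unadjusted change: variance 2(1 − ρ)σ²k², t on 46 df (2.013).
- ANCOVA: variance (1 − ρ²)σ²k² × (1 + 1/44), t on 45 df (2.014). The factor 1/44 = 1/(N − 4) is the expected cost of estimating the slope.
- Large-sample variance ratio, ANCOVA to unadjusted: (1 − ρ²)/[2(1 − ρ)] = (1 + ρ)/2.

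Example at ρ = 0.5: unadjusted width 2 × 2.013 × √1.00 × 0.306 = 1.233σ; ANCOVA width 2 × 2.014 × √(0.75 × 1.0227) × 0.306 = 1.080σ; 1.233/1.080 = 1.141.

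| ρ | Unadjusted width (σ) | ANCOVA width (σ) | Unadjusted wider by |
|---|---|---|---|
| 0.5 | 1.233 | 1.080 | 14.1% |
| 0.7 | 0.955 | 0.891 | 7.2% |
| 0.8 | 0.780 | 0.748 | 4.2% |
| 0.9 | 0.551 | 0.544 | 1.4% |
| 0.95 | 0.390 | 0.389 | 0.1% |

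Break-even is ρ = 0.953. At 28:14, the observed numbers that SAP Appendix D assumes for the primary endpoint, the excess at ρ = 0.5, 0.7, 0.8 and 0.9 is 13.9%, 7.0%, 4.0% and 1.2%, and break-even is 0.946. In 4,000 simulated trials per setting at 32:16, the ANCOVA interval was the narrower one in 97.7%, 89.0% and 57.3% of trials at ρ = 0.5, 0.7 and 0.9.

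**Gap between the two hemoglobin estimates.** With the same women and values, the gap is about (1 − ρ) times the chance Baseline imbalance, whose SD is 0.306σ. Its SD is 0.5 × 0.306 = 0.153σ at ρ = 0.5 and 0.2 × 0.306 = 0.061σ at ρ = 0.8. If the hemoglobin SD is 1.5 g/dL (an assumption; range 1.0 to 2.0), that is 0.23 g/dL (0.15 to 0.31) and 0.09 g/dL (0.06 to 0.12).

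**Opposite signs.** With no true effect the two estimates correlate at about √((1 + ρ)/2), so they disagree in sign in arccos(√((1 + ρ)/2))/π of trials: 16.7%, 12.7% and 10.2% at ρ = 0.5, 0.7 and 0.8. In simulation with a true effect of 0.5σ this falls to about 4%, 1% and under 1%.

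**The case against.** The strongest reply is that these tables are descriptive. SAP 9.3 and 9.4 plan no p-value, and Protocol 7.4 promises only a summary of laboratory values. Baseline is already visible in the baseline means, the shift tables and the plots of post-baseline against Baseline values, and safety review rests largely on toxicity grades and threshold criteria. That stands, and it limits the point to precision and consistency.

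Several stronger readings are tempting but not supported:

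- That the SAP has chosen raw differences. It never says unadjusted; this is inferred from silence, though it is the plain reading. If the sponsor meant something else, the method is unstated and needs the same sentence.
- That every safety interval is wider than the data allow. This depends on ρ, which no document gives, and the gain is gone near 0.95.
- That the unadjusted estimate is biased. Both estimators are unbiased under randomisation; they differ through chance imbalance, which the unadjusted interval already allows for.
- That power is lost. No safety test is planned, so a power figure would only illustrate precision.
- That opposite signs would mislead. This happens mainly when both estimates are near zero, and then almost never with either interval excluding zero.
- That iron supplementation argues for adjusting everything. It bears on hemoglobin alone.

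Nor are the two hemoglobin analyses identical apart from the covariate. The full analysis set groups women as randomised and the safety set as treated, and 9.3 admits local and SAE-triggered tests. This makes a rule on which result to read more useful.

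**Conclusion.** The point holds as a minor one. SAP 9.3 and 9.4 specify no Baseline adjustment for between-group differences in laboratory and vital-sign change, although Baseline is collected and the SAP adjusts for it elsewhere. The expected cost is intervals wider by about 14% to 4% for ρ from 0.5 to 0.8, about 1% at 0.9, and nothing above about 0.95. These figures rest on equal SDs, an assumed ρ, and full numbers at 32:16.

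The hemoglobin duplication does not depend on ρ: two between-group estimates are planned at Month 3 and Month 6, Baseline is worded differently for each, and nothing says which to interpret. The primary analysis already adjusts for Baseline menstrual blood loss, and its conclusion is unaffected.

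**What to change.** Replace the between-group part of the sentence in SAP 9.3 and 9.4 with wording such as:

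> The elagolix–placebo difference in change from Baseline at each visit, with its 95% CI, will be estimated by ANCOVA with treatment as the main effect and the Baseline value of that parameter as a covariate.

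Keep the raw within-group means, standard errors and intervals. For hemoglobin, adopt one Baseline definition across 8.4 and 9.3, including whether SAE-related and Day 1 pre-dose values count. Name the Section 8.4 ANCOVA as the hemoglobin comparison to be interpreted, and have 9.3 refer to it. Make the change before unblinding, so that the choice between two hemoglobin results is not made after seeing them.

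The cost is a few sentences, one covariate in the programs and one degree of freedom per analysis. No new data are needed. If the sponsor prefers unadjusted safety differences, the SAP should say so and label them descriptive; the hemoglobin changes are needed either way.

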Laboratory abnormalities will be evaluated based on Potentially Clinically Important (PCI) criteria as below. For each laboratory PCI criterion, the number and percentage of subjects who have a laboratory value meeting the criteria will be summarized by treatment

group. Listings will be provided to summarize subject-level laboratory data for subjects meeting PCI criteria.

The PCI criteria for lipid parameters during the Treatment Period are:

- Total cholesterol > 200 mg/dL
- LDL-C > 130 mg/dL
- LDL-C > 160 mg/dL
- HDL-C < 40 mg/dL
- TG > 150 mg/dL
- TG/HDL-C ratio > 3.5
- LDL-C/HDL-C ratio > 4.

Plots will be provided by treatment group for HDL-C, LDL-C, triglycerides, and hemoglobin during the Treatment Period:

- Final post-baseline lab values vs. Baseline lab values;
- Final post-baseline lab values vs. Baseline lab values for subjects with NCI CTC Grade 3 or 4;
- Worst post-baseline lab values vs. Baseline lab values;
- Worst post-baseline lab values vs. Baseline lab values for subjects with NCI CTC Grade 3 or 4

Plots will be provided by treatment group for HDL-C, LDL-C, and triglycerides during the Treatment Period:

- Mean percent change from Baseline in lipid parameters over time.

Plots of mean lab values over time during the Treatment Period will be provided for hemoglobin, total cholesterol, HDL-C, LDL-C, triglycerides (TG), LDL-C/HDL-C ratio, ALT, AST, bilirubin, apolipoprotein A and B.

Listings of subjects with at least one ALT/AST assessment meeting CTC grade 3 or 4 during the Treatment Period, subjects with at least one HDL C/LDL-C/TG/total cholesterol assessment meeting CTC grade 3 or 4 during the Treatment Period will be provided.

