## Appendix B. Definition of Adverse Events of Special Interest

Item of Safety Interest	Method of Surveillance
Hot flashes/night sweats	Non-bone related hypoestrogenic effects CMQ
Bone mineral density loss	Osteoporosis/Osteopenia SMQ DXA results from clinical trials
Anemia	Cases are identified through the Non-Hemolytic and Non-Aplastic Anemias CMQ Haematopoietic erythropenia SMQ
Bone Fractures	Osteoporosis/osteopenia SMQ Bone fracture CMQ
Rash and hypersensitivity reactions	Anaphylactic reaction SMQ Severe cutaneous adverse reactions SMQ Drug induced rash CMQ
Lipid abnormalities	Dyslipidemia SMQ
Uterine bleeding change	Female reproductive bleeds CMQ
Endometrial safety	Uterine and fallopian tube neoplasms, malignant and unspecified SMQ Reproductive Premalignant Disorders SMQ Endometrial biopsy results
Hypoestrogenic AEs (excluding hot flashes, BMD loss, and fractures)	Non-bone related hypoestrogenic effects CMQ
Spontaneous abortion	Termination of pregnancy and risk of abortion SMQ
Teratogenicity	Review of pregnancy outcomes All pregnancies will be followed up to 6 to 12 months post-delivery and reviewed at least quarterly and as they occur
Obstetrical complications (maternal and infant)	Pregnancy, labor, and delivery complications and risk factors (excluding abortions and stillbirths) SMQ
Psychiatric events	Depression and suicide/self-injury SMQ
Cardiovascular events	Cardiac arrhythmias SMQ, Cardiomyopathy SMQ, and Ischemic heart disease SMQ
Thromboembolic events	Embolitic and thrombotic events SMQ
Alopecia	Alopecia, diffuse alopecia, androgenic alopecia
Hepatic events	Drug related hepatic disorders comprehensive SMQ, Enhanced pharmacovigilance hepatic terms CMQ
Hormonally mediated malignancies	Breast neoplasms, malignant and unspecified SMQ Uterine and fallopian tube neoplasms, malignant and unspecified SMQ Ovarian neoplasms, malignant and unspecified SMQ

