**Appendix C. Exceptions to Standard CTC Lab Grading Criteria for Elagolix Studies**

ANALYTE	GRADE 1 TOXICITY	GRADE 2 TOXICITY	GRADE 3 TOXICITY	GRADE 4 TOXICITY
HEMATOLOGY				
EOSINOPHIL COUNT INCREASED*	650 – 1500 cells/mm 	1501 – 5000 cells/mm 	> 5000 cells/mm 	No Grade 4
HEMATOCRIT DECREASED**	Decrease in > 0% – 5% below LLN or below BL if BL below LLN	Decrease in > 5% – 10% below LLN or below BL if BL below LLN	Decrease in > 10% below LLN or below BL if BL below LLN	No Grade 4
WHITE BLOOD CELL COUNT INCREASED*	10,800 – 15,000 cells/mm 	> 15,000 – 20,000 cells/mm 	> 20,000 – 25,000 cells/mm 	> 25,000 cells/mm 
CHEMISTRIES				
BUN**	1.25 – 2.5 × ULN	> 2.5 – 5.0 × ULN	> 5 – 10.0 × ULN	> 10 × ULN
LDL CHOLESTEROL HIGH***	130 – 159 mg/dL	≥ 160 – 189 mg/dL	≥ 190 mg/dL	No Grade 4
HDL CHOLESTEROL LOW***	Low abnormal: < 40 mg/dL***			
PROTEIN, SERUM, LOW*	5.5 – 6.0 g/dL	5.0 – < 5.5 g/dL	< 5.0 g/dL	No Grade 4

\* US Department of Health and Human Services Food and Drug Administration Center for Biologics Evaluation and Research. September 27. Guidance for Industry Toxicity Grading Scale for Healthy Adult and Adolescent Volunteers Enrolled in Preventative Vaccine Clinical Trials.

\*\* Elagolix program criteria based on patient population, the disease states under study, and previous clinical trial experience.

\*\*\* National Institutes of Health National Cholesterol Education Program; Detection Evaluation and Treatment of High Blood Cholesterol in Adults (Adult treatment Panel III) Final Report NIH Publication No. 02-5215 September 2002.

[figure not shown]
National Cancer Institute's Common Terminology Criteria for Adverse Events (NCI CTC) is applied to all hematology and chemistry analytes across the elagolix program where quantitative criteria are available. In the CTC where similar quantitative values are assigned to multiple grades and a qualitative criterion distinguishes between the grades, the more conservative quantitative grade is applied.

The table above includes those instances where CTC criteria are not provided for applicable lab parameters and alternative references are applied.

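### The lipid PCI table counts any on-treatment value past a cut-off without regard to Baseline, so new and pre-existing abnormalities are mixed; for three of the seven criteria no planned summary is set to separate them

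*SAP*

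**What the plan says.** SAP 9.3, under Laboratory Data in the Treatment Period, defines the PCI table: "For each laboratory PCI criterion, the number and percentage of subjects who have a laboratory value meeting the criteria will be summarized by treatment" group. The list opens with "The PCI criteria for lipid parameters during the Treatment Period are" and gives seven fixed cut-offs: total cholesterol > 200, LDL-C > 130, LDL-C > 160, HDL-C < 40 and TG > 150 mg/dL, TG/HDL-C > 3.5, and LDL-C/HDL-C > 4. Neither the counting sentence nor the list mentions the Baseline value. A subject-level listing is planned for women who meet a criterion.

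The same section also plans outputs that do use Baseline:

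- mean change in lipid variables, with the between-arm difference and 95% CI, including both ratios above;
- shift tables from Baseline to the worst and to the final value, for selected parameters;
- lipid category counts at Baseline and at each visit, by arm;
- plots of worst and final value against Baseline for HDL-C, LDL-C, triglycerides and hemoglobin.

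Protocol 5.1 sets numeric limits for hemoglobin, creatinine, transaminases, bilirubin and FSH, but none for lipids. Criterion 13 and Operations Manual 3.8 leave other laboratory abnormalities to a judgment of clinical significance.

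**The concern.** A count of women with an important on-treatment value will be read as a count of what happened on treatment. As written, it also takes in women who entered with the abnormality. A woman whose LDL-C stays at 140 mg/dL throughout, or falls from 170 to 135, is counted under LDL-C > 130 exactly as is a woman who rises from 110 to 140.

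Women who met the criterion before dosing add similar amounts to both arms on average, so they raise both percentages and shrink the difference and the ratio between them. With 16 women planned on placebo, they also add noise, because the number past a cut-off at entry can differ between arms by chance. Lipid abnormality is among the SAP's items of safety interest (Appendix B), so the table is likely to be read for a drug effect.

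**Working it through.** **No plan figure to reproduce.** The documents give no lipid prevalence, onset rate or expected PCI percentage. The only document inputs are the arm sizes, 32 and 16 (SAP 2.4). Every rate below is an assumption.

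**Step 1: which criteria can be separated by Baseline status elsewhere in SAP 9.3?**

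| PCI criterion | By-visit category boundary, including Baseline | Worst-vs-Baseline plot |
|---|---|---|
| LDL-C > 130 | 130 (≥ rather than >) | yes |
| LDL-C > 160 | 160 (≥ rather than >) | yes |
| HDL-C < 40 | 40 | yes |
| TG > 150 | 150 | yes |
| Total cholesterol > 200 | lowest is 300 | no |
| LDL-C/HDL-C > 4 | 3 | no |
| TG/HDL-C > 3.5 | none | no |

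Four criteria have a matching or nearly matching Baseline category, and three have none. Even for the four, the category counts are marginal: they show how many women are past the boundary at Baseline and at each visit, not how many crossed it. Shift tables do show crossings, but by CTC grade or laboratory normal range and for parameters that the sentence does not name. Appendix C grades LDL-C at 130, 160 and 190 mg/dL, so an LDL-C shift table would come close to the PCI cut-offs. It grades neither ratio. For total cholesterol, a normal-range shift table would serve only if that analyte is selected and the laboratory's upper limit is 200; the documents state neither.

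**Step 2: form of the dilution.** Let b be the proportion meeting a criterion at Baseline, s the proportion of those who still meet it on treatment (equal in both arms), and i the new-onset rate among the rest. The counted proportion is

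P = b·s + (1 − b)·i.

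The b·s term cancels in the difference, so the counted risk difference is (1 − b)·(i_elagolix − i_placebo).

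**Step 3: two assumed scenarios at b = 30%.**

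- Onset 15% v 5%, s = 100%: 0.30 + 0.70 × 0.15 = 40.5%, and 0.30 + 0.70 × 0.05 = 33.5%. The counted difference is 7 points against 10 among women at risk. Pre-existing share of elagolix cases: 0.30/0.405 = 74%.
- Onset 30% v 10%, s = 90%: 0.27 + 0.21 = 48%, and 0.27 + 0.07 = 34%. The counted difference is 14 points against 20, and the ratio is 1.41 against 3.0. Pre-existing share of elagolix cases: 0.27/0.48 = 56%.

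In the second scenario, the ratio is 2.0 at b = 10%, 1.62 at 20% and 1.20 at 50%.

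**Step 4: chance imbalance at entry.** SD = √[b(1 − b)(1/32 + 1/16)]. At b = 30% this is √(0.21 × 0.09375) = 0.140, or 14 points.

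**Step 5: effect on the direction of the table.** Simulating trials at 32:16 with b = 30%, the probability that elagolix shows a lower percentage than placebo, although its true onset rate is higher, is:

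| Onset | All-subject count | Women at risk only |
|---|---|---|
| 15% v 5%, s = 100% | 28% | 14% |
| 30% v 10%, s = 90% | 15% | 7% |

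For the first scenario, the pairs are 21% v 12% at b = 15% and 31% v 15% at b = 40%.

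**The case against.** The strongest reply is that this is one table among several. The mean-change analysis covers total cholesterol and both ratios with a between-arm interval. Baseline imbalance is visible for four of the seven criteria, and the plots for LDL-C, HDL-C and TG show individual movement. All of that stands. A reader might infer that the plan as a whole could hide or reverse a lipid effect; the documents do not support that, because these other outputs are not diluted in this way.

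A reader might also extend the point to the grade 3–4 summary. That rests only on silence in one line: "Laboratory abnormalities meeting CTC criteria grade 3 and 4 will be summarized". CTC shift tables and Baseline plots restricted to grade 3–4 subjects are planned, hematocrit grade 3 refers to Baseline when Baseline is low ("Decrease in > 10% below LLN or below BL if BL below LLN"), and Appendix C gives HDL-C one ungraded level ("Low abnormal: < 40 mg/dL"). The point is not made for that summary.

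Nor is absolute counting inconsistent in itself. In SAP 9.4 six of the nine vital-sign criteria pair a threshold with a change, but three (diastolic ≥ 100 mmHg, systolic ≥ 160 mmHg, pulse ≥ 120 bpm) are absolute. For ALT, AST and bilirubin the SAP says outright that Baseline is disregarded. For lipids it simply does not say. Surveillance of lipid abnormality in Appendix B runs through the "Dyslipidemia SMQ", not through PCI counts.

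Finally, counting only women at risk would lose those already past a cut-off who worsen, and at 40% prevalence it would leave about 10 placebo women (16 × 0.6 = 9.6). That is a good reason to keep the all-subject count, not to leave it unsplit. The PCI listing does not close the gap: it covers only women who meet a criterion, so it supplies no at-risk denominator, and the SAP does not say that it flags Baseline status.

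**Conclusion.** The point holds for the lipid PCI table. As written, its percentages combine pre-existing and new abnormalities, and the contrast between arms in that table is diluted. For "Total cholesterol > 200 mg/dL", LDL-C/HDL-C > 4 and TG/HDL-C > 3.5, no planned table or plot is set to show how many women newly met the criterion. For the other four, the by-visit counts are marginal, and crossings must be read from plots or, for LDL-C, from a shift table if it is among the selected parameters.

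The size is not derivable from the documents. What follows without assumed rates is the form: with equal persistence, the risk difference is multiplied by (1 − Baseline prevalence). The 14-point SD of chance imbalance needs an assumed 30% prevalence, and the wrong-direction probabilities depend further on assumed onset and persistence; the two scenarios differ about twofold. Randomization balances pre-existing cases in expectation only.

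Severity is low. The table is descriptive, the primary analysis is untouched, and nothing here bears on clinical management.

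**What to change.** In SAP 9.3, keep the all-subject PCI count and add to the same table, by arm and for each of the seven lipid criteria:

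1. the number of women meeting the criterion at Baseline;
2. the number and percentage newly meeting it in the Treatment Period, with denominator the women whose Baseline value does not meet it and who have at least one post-baseline value in that period.

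Use the same Baseline value as the mean-change tables, and flag Baseline status for each criterion in the PCI listing.

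The cost is a few lines of SAP text and one filter in the table program. No new data are needed: the Protocol Appendix D schedule already has lipid panels at Screening, Day 1, Month 3, Month 6 and premature discontinuation. The downside is that the new-onset denominators are smaller and differ by criterion, so they must be printed with each percentage.
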